3.1.3 Dose escalation for dose panel and stopping rules

Decisions regarding dose escalation will be made based on the review of all cumulative safety information which includes, in general, the safety data through study Day 15 from the 10 subjects in the preceding lower dose cohort. If neither of the below stopping rules is present in dose panel, then dose escalation may proceed within the next higher dose level. However, escalation to the next higher cohort may occur when none of the stopping rules have been met and no less than 5 subjects in a cohort have been followed for at least 2 weeks under certain conditions as illustrated in [section 3.1.4](#).

The stopping rules listed below will be used to determine whether it is safe to escalate to the next higher cohort. Dose escalation to the next planned dose will not proceed if any of the following criteria are met (Adverse event grading as defined by the Common Terminology Criteria for Adverse Events [CTCAE, Version 4.0]):

- Five or more subjects in a cohort have platelet counts $>450,000/\text{mm}^3$ for non-splenectomized subjects and $>600,000/\text{mm}^3$ for subjects who underwent splenectomy, and platelet count raise is not attributable to a rescue or concomitant therapy.
- Two or more subjects have serious adverse events in the same organ system (Grade 3 and above), that are determined to be related to study medication,
- It is determined that the limit of safety and/or tolerability has been reached. This decision will be made following discussions between the Study Team and the Investigator,

If any of the above criteria are met within a dose level, the progression to a higher dose level will be put on hold and all safety data available across the study will be evaluated to estimate the risk of proceeding to the higher dose level. The review will include all of the subject(s) that experienced SAEs listed above. In addition, data set may include subjects from a dose panel, the entire dose panel, or if appropriate, all randomized subjects treated to date.

In addition, decision may be made following discussions between the Study Team and the Investigator to halt dose escalation for reasons not defined above, including but not limited to, observing a single serious adverse event in individual subjects, observing trends in a given dose panel and across dose panels, and/or it is determined that the limit of safety and/or tolerability has been reached.

[figure not shown]
If dose escalation is stopped due to any of these findings, additional cohorts may receive the same or lower doses of the investigational compound.

At the time of dose escalation, dose levels of new cohorts may be adjusted to lower doses if the accumulated safety data so dictates.

Adaptive dose selection may be performed to adjust some pre-selected doses, e.g., the third or/and fourth cohort doses, using accumulated efficacy and dose or exposure data. Models based on response rate, such as but not limited to (Bayesian) logistic regression, (Bayesian) EMax, may be utilized to predict a dose satisfying certain efficacy criteria, which might be different from the standard. If there are enough responding subjects with multiple platelet measurements, changes of platelet count may be directly modeled by dose and study day to facilitate dose prediction. The selected dose for a cohort should not exceed the originally planned dose for that cohort, i.e., selected dose for cohort C should not be larger than 675mg and it should be at most 1500 mg for cohort D.

The study design schematic is presented in [Figure 3.1.3-1](#).

Figure 3.1.3-1: Study Design Schematic: Short-term period

*Will not apply to subjects entering LTE

Figure 3.1.3-2: Study Design Schematic: Short-term period

Intra-Subject Dose Escalation

[figure not shown]
[figure not shown]

Figure 3.1.3-3: Study Design Schematic: Long term extension period

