1.5 Overall Risk/Benefit Assessment

BMS-986004 is currently being evaluated in humans in a FIH SAD study which is being performed in healthy subjects to investigate the safety, tolerability, PK and PD of BMS-986004. To-date, BMS-986004 has not been studied in the ITP patient population and hence no efficacy or benefit data is established for this population. However, no clinically significant risks have been identified in the FIH study to-date and the safety margins in non-clinical studies are favorable which justifies careful evaluation of BMS-986004 in the ITP patient population. BMS-986004 could potentially provide clinical benefit by normalizing platelet counts in patients with ITP. This study will be initiating at a dose that has demonstrated relatively low immunosuppressive effect and has demonstrated no clinically significant risks in the FIH study. Dose panels will be enrolled sequentially in an ascending manner upon careful review of all cumulative safety information. Cumulative safety data will include all additional data that is available in the FIH study as well as data collected during the ITP study. To manage the safety risks, careful clinical and laboratory monitoring and criteria relative to dose escalation and stopping rules have been established for this protocol and include thresholds for serious infections, liver function tests, platelet counts above established thresholds, and other adverse events.

It is expected that ITP subjects will derive clinical benefit from BMS-986004 and help guide dose selection and design of future studies in the clinical development of BMS-986004. Primary efficacy assessments will include the proportion of patients achieving platelet count at least $\geq 30,000/\text{mm}^3$ and at least 2-fold increase from the baseline count and absence of bleeding.

The subjects planned to be enrolled in this study have limited therapeutic options since they have failed conventional therapies including immunosuppressive therapies, splenectomy and TPO mimetics. It is anticipated that efficacious doses of BMS-986004 will provide long lasting

therapeutic benefit for ITP patients. Ultimately, targeting CD40L may provide opportunity to inhibit autoimmune processes leading to thrombocytopenia and induce durable disease remission. It may thus offer novel therapeutic modality, currently not available to patients.

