1.5.1 Potential risks associated with BMS-986004

BMS-986004 is a dimeric anti-human CD40L VH dAb formatted with the Fc-tail from abatacept (modified IgG1) that is entirely inert in Fc effector function, especially in context of FcγRIIIa. All data from nonclinical and NHP studies demonstrate that BMS-986004 exhibited no activity in various platelet activation assays, as well as in direct biacore binding analysis with FcγRIIIa. Based on previous clinical experience with antibodies targeting costimulatory molecules and in particular with anti-CD40L antibodies, potential risks include: (1) increased probability of TE; (2) an increase in susceptibility to infection and (3) immunogenic potential including infusion reactions and formation of ADA. In addition to conventional safety assessments, general risk mitigation plan includes the following:

- To initiate dosing at 75 mg dose that has demonstrated favorable safety profile in healthy subjects in clinical evaluation. This dose is expected to elicit a sub-optimal response while ensuring very good safety profile.
- To utilize safety criteria for intra-subject dose escalation and safety criteria for dose-panel escalation and stopping rules.

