3.1.4 Early decision of dose escalation for dose panel

When a cohort is filled and a new subject is available to be treated, an early decision can be made on whether to open the next higher cohort if not all the subjects have completed the evaluation period. The early decision rule is based on controlling the probability of making a wrong early decision, called decision risk, to be at most 15%. Detailed information on deriving the decision risk is included in [Appendix 1](#).

The early decision rule is based on the largest number of subjects who developed AE of interest which is drug-related SAE within the same organ system at grade 3 or higher. The early decision does not directly take into consideration other criteria as covered by the stopping rule. As such, its decision can be modified upon agreement from both investigators and sponsor. In case subjects are allocated to the higher cohort and at least one stopping rule as stated above is triggered toward the lower dose cohort when more events are observed at the lower cohort, decision will be made upon agreement from both investigators and sponsor after considering all safety data.

Three count numbers are used by the decision rule and are defined as follows.

- Titration-Dose Evaluable Subjects (nH): the number of subjects who are titrated and complete the evaluation period (2 weeks) starting from the first titration dose (on day 43).
- Start-Dose Evaluable Subjects (nL): the number of subjects who develop drug related SAE at grade 3 or higher or complete the evaluation period (2 weeks) from the first dose (on day 1) but haven't completed the 2 weeks evaluation period following the first titration dose (on day 43) if being titrated to a higher dose.
- Subjects with AE of Interest (k): the largest number of subjects who developed drug-related SAE within the same organ system at grade 3 or higher, which could happen any time after the first dose of BMS-986004 till the decision making day. The value of k is allowed to be either 0 or 1. Note that it doesn't distinguish at which stage of treatment, prior to or post titration, that such AE happened.

Minimum Requirement for Cohort Escalation

A set of minimum safety requirement, as listed below, must be met in order to make an early decision.

- There must be at least 5 (nL+nH>=5) safety evaluable subjects (with safety data through study Day 15)
- A higher dose than the new cohort’s start dose must be shown tolerated in the IM140-002 study.

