APPENDIX 1 ADAPTIVE EARLY DECISION FOR DOSE PANEL ESCALATION

Introduction

A model-based cohort escalation rule is established to help decide on opening the next cohort for newly enrolled subjects when current cohort is filled but not all of its subjects are monitored for 2 whole weeks regarding drug toxicity and tolerability. The decision rule would allow treating subject, once available, at the next cohort without waiting for the completion of every subject's AE evaluation period at the current cohort and at the same time keeping decision risk acceptably low.

Please note that AE would be closely monitored throughout the trial for each subject, and the 2 weeks' AE evaluation period mentioned here is for the purpose of cohort escalation only. During the evaluation period, the numbers of subjects who developed drug-related SAE within the same organ system at grade 3 or higher, called AE of interest are counted and the largest number will be used.

Decision Risk

The decision risk is mathematically defined as the probability of observing enough number of event(s) in the still non-evaluable subjects given data collected from evaluable subjects such that cohort escalation is not allowed. Evaluable subjects are those who are observed an AE of interest or complete the AE evaluation period. To enroll subject into the next cohort, the non-adaptive cohort escalation rule requires, among others, no more than one subject being reported drug-related serious adverse event or serious infection and infestation within the evaluation period. Therefore, if one subject is observed with an AE of interest, the decision risk would be the probability of observing at least one more AE of interest in the non-evaluable subjects; if no AE of interest is reported, the decision risk is thus the probability of observing at least two AEs of interest from the non-evaluable subjects.

Decision Data

To take advantage of the titration design, in which subjects could possibly take a higher dose that is to be used initially in the next cohort, the adaptive decision rule makes use of the following three statistics:

- Titration-Dose Evaluable Subjects (nH): the number of subjects who are titrated and complete the evaluation period (2 weeks) starting from the titration's first dose (on day 43).

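### The numeric SAE stop counts events only within an undefined organ system, so two related serious thromboembolic events at different sites need not make the escalation hold mandatory

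*Protocol*

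**What the plan says.** Section 3.1.3 of the protocol, repeated in the synopsis, lists three criteria, any of which blocks escalation. The first counts subjects with high platelet counts. The second is the only numeric SAE criterion: "Two or more subjects have serious adverse events in the same organ system (Grade 3 and above", restricted to events judged related to study drug. The third is a judgement that the limit of safety or tolerability has been reached. A further paragraph allows, but does not require, a halt for other reasons, including a single SAE or "observing trends in a given dose panel and across dose panels".

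Section 3.1.4 lets the next cohort open early. Its count k is "the largest number of subjects who developed drug-related SAE within the same organ system at grade 3 or higher", so it is the highest within-system count and not a total. Two subjects trigger the stop. With k = 1, Table 3.1.4-1 decides between wait and escalate. The section adds that "its decision can be modified upon agreement from both investigators and sponsor".

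The rule does not define organ system. Protocol sections 5.3 and 8.4.3 and SAP section 7.6 tabulate adverse events by system organ class, and SAP section 7.1 codes them in MedDRA, but no text ties the stopping rule to that classification.

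Section 1.5.1 lists the potential risks of the drug, starting with "1) increased probability of TE". Section 1.5.2 gives TIA, stroke, pulmonary embolism and deep vein thrombosis as examples of thromboembolic disease.

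Two other places describe the rule differently. Appendix 1 defines its event as "drug-related SAE within the same organ system at grade 3 or higher, called AE of interest", but then summarises the non-adaptive rule as requiring "no more than one subject being reported drug-related serious adverse event or serious infection and infestation within the evaluation period", with neither the organ-system nor the grade limit. Section 1.5 says that "stopping rules have been established for this protocol and include thresholds for serious infections, liver function tests". Section 3.1.3 lists neither an infection threshold nor a liver-test threshold.

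**The concern.** A within-system count works when a drug's harm shows itself in one organ. TE is one suspected mechanism that can appear in the brain, the lung or the limbs. The protocol makes a hold compulsory for two related serious events that it treats as alike. For two related serious events of its first-named risk, the hold may depend on how the sites are classified, and the text does not settle that. Two careful readers could apply the numeric rule to the same panel and reach opposite answers. At stake is whether the next cohort can open at a higher dose without the numeric rule having forced a pause.

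**Working it through.** **1. The plan's own figures.** Appendix 1 gives the decision risk for k = 1. I took independent Beta(0.01, 0.49) priors at the start dose and the next dose, ordered so that the lower dose has the lower rate, with the single event at the start dose. Risk = E[1 - (1 - pL)^(10 - nH - nL)], where pL is the start-dose rate.

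| nH / nL | Appendix 1 | Recomputed |
|---|---|---|
| 0 / 9 | 8.3% | 8.2% |
| 0 / 8 | 16.6% | 16.7% |
| 0 / 5 | 43.2% | 43.0% |
| 1 / 8 | 7.2% | 7.2% |
| 4 / 5 | 6.2% | 6.2% |
| 8 / 1 | 5.7% | 5.5% |

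The table reproduces within simulation error. The question is what k counts, not how the risk is computed.

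**2. Two TE events in different systems.** One related Grade 3+ stroke and one related Grade 3+ pulmonary embolism, classed to different systems, give counts of 1 and 1. The largest is 1, so criterion 2 is not met and k = 1. Table 3.1.4-1 then reads escalate in all 9 cells with 9 evaluable subjects, in 7 of the 8 cells with 8, and in none with 7 or fewer. With all 10 evaluable, no numeric SAE rule blocks escalation.

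**3. How often.** The documents give no TE rate and no split over organ systems, so both are assumptions. Let p be the chance that a subject has a related Grade 3+ TE SAE (at most one each), n = 10, and w_j the share falling in system j.

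- TE pooled: P(hold) = 1 - (1-p)^10 - 10p(1-p)^9.
- Current rule, TE events only: P(hold) = 1 - sum over subsets S of systems of [10!/(10-|S|)!] × product over S of (p w_j) × (1-p)^(10-|S|).
- Gap = pooled - current. Share not held = gap / pooled.

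Example, p = 0.05 with four equal systems. Pooled: 1 - 0.5987 - 0.3151 = 0.0861. Current: 1 - (0.5987 + 0.3151 + 0.0560 + 0.0039 + 0.0001) = 0.0261. Gap 0.0600; share 0.0600/0.0861 = 69.6%.

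| p | Pooled hold | Quantity | 80/20 | 2 equal | 3 equal | 4 equal |
|---|---|---|---|---|---|---|
| 1.7% | 1.19% | Gap, points | 0.36 | 0.57 | 0.77 | 0.87 |
| | | Share not held | 30.5% | 47.7% | 64.6% | 73.3% |
| 5% | 8.61% | Gap, points | 2.39 | 3.73 | 5.21 | 6.00 |
| | | Share not held | 27.7% | 43.3% | 60.5% | 69.6% |
| 10% | 26.39% | Gap, points | 6.20 | 9.69 | 14.19 | 16.79 |
| | | Share not held | 23.5% | 36.7% | 53.8% | 63.6% |

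With exactly two TE subjects the share not held is 1 - sum of w_j²: 32%, 50%, 67% and 75% for the four splits. The 75% is the upper end as the rate approaches zero.

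**4. Two corrections that lower the gap.**

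- *Window.* The 1.7% is 12/721 from Appendix 1: all drug-related SAEs over half a year in an abatacept study. It is neither a TE rate nor a bound. Cohort review is in general on data through Day 15. At constant hazard, 1.7% × 14/182 = 0.13%, and the gap becomes 0.002-0.006 points. This is a low-end case, because k counts events up to the decision day and some subjects will have longer follow-up.
- *Non-TE events.* Criterion 2 counts every related Grade 3+ SAE, so a non-TE event plus a TE event in the same system can already trigger it. With an assumed independent 5% background rate spread equally over the same four systems, and TE events still counted in their own system, the gap falls from 6.0 to about 4.7 points at p = 5%, and from 16.8 to about 13 points at p = 10%.

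**The case against.** The strongest reply is that a hold adds little. Under section 3.1.3 a hold leads to a review of all safety data, and review before escalation is already compulsory: section 3.1.3 bases the decision on cumulative safety data, section 5.6.1 requires real-time TE-biomarker review for go/no-go decisions, and section 7 has the DMC review preceding cohorts before the next one opens. The third criterion binds once it is judged to be met, and a single SAE can halt escalation. For the gap to matter, all of these would have to pass over two related serious TE events in ten subjects.

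This limits the consequence. It does not close the gap, because none of these safeguards states a TE count in the documents provided (the DMC charter is not among them), and a numeric rule exists so that a hold does not depend on case-by-case judgement.

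Three further objections stand. No document assigns stroke, TIA, pulmonary embolism or deep vein thrombosis to an organ system, so the split is conditional; if the team classed all TE as one system, the rule would trigger. The 5% and 10% rates are assumptions. The gaps in the main table are upper figures, for the two reasons given with the calculation.

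A reader might infer that escalation would follow automatically after two TE events. The documents do not support that: Table 3.1.4-1 can be overridden and the discretionary routes remain. A reader might also infer from the Appendix 1 summary sentence that any two related SAEs already bar escalation. Taken alone it says so, but the same appendix defines the event with both limits and computes the risk on that definition, and section 3.1.3 is the operative rule. The sentence is an inconsistency, not a second safeguard.

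**Conclusion.** The point holds in a limited form. If TE events at different sites are classed to different systems, two related serious TE events in a panel give k = 1, and the hold is discretionary rather than required by the numeric rule. Roughly 24-75% of 10-subject panels with two or more TE subjects would not meet criterion 2 through TE events alone; this share depends mainly on the assumed split and less on the rate. The absolute gap depends strongly on the assumed rate: under 1 point per panel at 1.7%, near zero if that rate is scaled to 14 days, at most about 2-6 points at 5% and 6-17 points at 10%, and lower once non-TE SAEs are counted. It would be wrong to read this as an absence of oversight of TE. It is a gap in the mandatory part of the rule, for the drug's first-named risk, that is cheap to close.

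**What to change.** 1. In criterion 2 and in the definition of k (sections 3.1.3 and 3.1.4, synopsis, Appendix 1), count all arterial and venous thromboembolic SAEs as one category regardless of organ system. Keep the grade, relatedness and two-subject threshold. Let each event also keep its place in its own organ system, so that no hold under the present rule is lost.
2. For all other events, define organ system as the MedDRA system organ class already used for the adverse event tables.
3. Reconcile the Appendix 1 summary sentence and section 1.5 with section 3.1.3. Either add the serious-infection and liver-test thresholds that section 1.5 says exist, or state that these events count only through criterion 2. Do not drop the infection wording silently.

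The cost is a sentence or two in each place and one explicit decision on the infection and liver thresholds. No new data are needed, because the SAEs are already collected. The downside is a few more holds, at most the gaps shown above. Over three escalation decisions, taking panels as independent with the same rate, the chance of at least one extra hold is 1 - (1 - gap)^3: at most 1.1-2.6% at 1.7%, 7.0-16.9% at 5% and 17.5-42.4% at 10%. An extra hold leads to a review of safety data, not to the end of the study.

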3.1.4 Early decision of dose escalation for dose panel

When a cohort is filled and a new subject is available to be treated, an early decision can be made on whether to open the next higher cohort if not all the subjects have completed the evaluation period. The early decision rule is based on controlling the probability of making a wrong early decision, called decision risk, to be at most 15%. Detailed information on deriving the decision risk is included in [Appendix 1](#).

The early decision rule is based on the largest number of subjects who developed AE of interest which is drug-related SAE within the same organ system at grade 3 or higher. The early decision does not directly take into consideration other criteria as covered by the stopping rule. As such, its decision can be modified upon agreement from both investigators and sponsor. In case subjects are allocated to the higher cohort and at least one stopping rule as stated above is triggered toward the lower dose cohort when more events are observed at the lower cohort, decision will be made upon agreement from both investigators and sponsor after considering all safety data.

Three count numbers are used by the decision rule and are defined as follows.

- Titration-Dose Evaluable Subjects (nH): the number of subjects who are titrated and complete the evaluation period (2 weeks) starting from the first titration dose (on day 43).
- Start-Dose Evaluable Subjects (nL): the number of subjects who develop drug related SAE at grade 3 or higher or complete the evaluation period (2 weeks) from the first dose (on day 1) but haven't completed the 2 weeks evaluation period following the first titration dose (on day 43) if being titrated to a higher dose.
- Subjects with AE of Interest (k): the largest number of subjects who developed drug-related SAE within the same organ system at grade 3 or higher, which could happen any time after the first dose of BMS-986004 till the decision making day. The value of k is allowed to be either 0 or 1. Note that it doesn't distinguish at which stage of treatment, prior to or post titration, that such AE happened.

Minimum Requirement for Cohort Escalation

A set of minimum safety requirement, as listed below, must be met in order to make an early decision.

- There must be at least 5 (nL+nH>=5) safety evaluable subjects (with safety data through study Day 15)
- A higher dose than the new cohort’s start dose must be shown tolerated in the IM140-002 study.

Early Decision Rule:

If there is not AE of interest observed, the early decision rule is the same the minimum requirements.

If there is one AE of interest observed, the early decision rule is shown below in Table 3.1.4-1, where W represent wait, i.e., not enough evidence to enable dose panel escalation, and E represents escalate.

If there are least two subjects with AE of interest, stopping rule is triggered, and subject cannot be treated at the next higher cohort.

Table 3.1.4-1: Decision Rule for Early Panel Escalation When There Is One Subject with AE of Interest (k=1)

Titration-Dose Evaluable Subjects (nH) ^a	Start-Dose Evaluable Subjects (nL) ^b								
	1	2	3	4	5	6	7	8	9
0	W ^c	W	W	W	W	W	W	W	E ^d
1	W	W	W	W	W	W	E	E	
2	W	W	W	W	W	E	E		
3	W	W	W	W	E	E			
4	W	W	W	E	E				
5	W	W	E	E					
6	W	E	E						
7	E	E							
8	E								

^a the number of subjects who are titrated and complete the evaluation period (2 weeks) starting from the titration’s first dose.

^b the number of subjects who develop AE of interest or complete the evaluation period (2 weeks) from the first dose but could not be classified into the “Titration-Dose Evaluable Subjects” group.

^c W: Wait

^d E: Escalate

Physical examinations, vital sign measurements, 12-lead electrocardiograms (ECG), and clinical laboratory evaluations will be performed at selected times throughout the dosing interval. Subjects will be closely monitored for adverse events throughout the study. Blood samples will be collected for up to 336 hours after study drug administration for pharmacokinetic (PK)

analysis. Approximately 910 mL of blood will be drawn from each subject during the short-term period (~162 days including Screening and follow up period). Less than 500mL of blood will be drawn during the LTE period.

The approximate duration of the short-term period is 23 weeks (approximately 162 Days). This includes a 21 day screening period, a 12 week treatment period and a 2 month follow up period. An extended screening period (up to 42 days) is possible but only with the approval of the Study Director, and all other eligibility rules and screening rules must still be met. If subject is eligible and opts to continue into LTE, the 2 month follow-up period will not be performed after the short-term period is completed and the subject will enter the LTE directly. If the subject opts not to enter the LTE, then a 2 month follow-up visit will be completed.

The approximate duration of the long term extension is approximately 55 weeks. This includes 24 weeks of every other week dosing of 1500 mg, two-taper visits (7 weeks total), and a 24 week follow-up period (no treatment).

